3.2. Eligibility Criteria for Subject Selection

The inclusion and exclusion criteria for subject selection can be found in Amendment 05 to Clinical Study Protocol EN3319-304, Section 9.

3.3. Study Drug Administration

Subjects in Groups A and B received oxymorphone HCl immediate-release liquid 1 mg/mL 0.05 mg/kg orally (or an oral liquid placebo matched in color and flavor for multiple-dose phase) with subsequent dose to be determined by IDMC. It was intended that the subjects in Groups C and D would receive oxymorphone HCl IV solution 1 mg/mL at doses to be determined by IDMC (or a matched placebo appropriate for parenteral administration). However, by the time Group B was to enroll subjects in single-dose phase, the study was suspended (only 5 subjects were enrolled in Group B for cohort 1).

The selection of dose has been described in the study design section and the timing of drug dosing will be as presented in Table 1 and Table 2 (Schedule of Events for single-dose and multiple-dose phases).

3.3.1. Determination of Sample Size

The sample size of the study was based on the assumptions of both efficacy and PK endpoints. The planned number of subjects for single-dose phase and multiple-dose phase are as follows:

- For the single-dose phase, 5 subjects from each age group (i.e. up to total of 60 subjects) were to receive oxymorphone depending on IDMC recommendations.
- For the multiple-dose phase, 10 subjects from each age group (i.e. total of 40 subjects) were to be randomized to receive either oxymorphone or placebo.

3.3.1.1. Efficacy

The efficacy sample size was determined based on primary analysis to compare cumulative morphine demand via NCA during the multiple-dose phase. To detect a difference in effect size of 0.9, 20 subjects for each group (active treatment group pooled across all age groups vs. placebo group pooled across all age groups) would have 80% power at 2-sided significance level of 0.05.

3.3.1.2. Pharmacokinetics

In earlier PK modeling it was indicated that the best fitting model was 2 compartmental and that the inter and intra-subject coefficient of variation (CV[%]) for clearance and volume of distribution were 54% and 20%, respectively. The sample size of the PK sample was determined based on the assumption that if each subject provides 3 data points in the ranges of absorption and terminal elimination phases, the total CV(%) (combination of the inter- and intra-subject CV[%]) is approximately 60%. Based on this assumption, a total of 34 subjects are needed to provide estimates of clearance and volume of distribution if their 95% confidence interval is within the range of 0.6 to 1.4 of the point estimates with 90% power.

3.3.2. Blinding and Randomization

3.3.2.1. Randomization

Subjects were to be stratified by 4 different age groups as outlined in Table 3 and Table 4. During the multiple-dose phase, subjects within each age group were randomized to receive either oxymorphone HCl or placebo in a 1:1 allocation ratio.

Table 3: Treatment Assignment – Single-Dose Phase

Age Group	Oxymorphone HCl (Max N)
6 months – <2 years (up to and inclusive of 729 days)	15
61 days – <6 months (up to and inclusive of 179 days)	15
31 days – 60 days	15
0 – 30 days	15
Total	60

Table 4: Treatment Assignment – Multiple-Dose Phase

Age Group	Oxymorphone HCl (N)	Placebo (N)
6 months – <2 years (up to and inclusive of 729 days)	5	5
61 days – <6 months (up to and inclusive of 179 days)	5	5
31 days – 60 days	5	5
0 – 30 days	5	5
Total	20	20

3.3.2.2. Blinding

The multiple-dose phase of this study was double-blinded. Subjects, parents, study staff, clinical staff, vendor staff with the exception of the packaging and labeling vendor, and the Sponsor (with the exception of the clinical supplies staff) and its designees were blinded to the study treatment being received by each subject.

3.4. Efficacy Assessments

The SAP for this abbreviated CSR includes safety assessments only. All efficacy endpoints and efficacy assessments planned in the protocol were removed. This change is included in the Change from Protocol Section of the SAP.

3.5. Medical and Surgical History

A medical and surgical history of the subject was collected during Screening. Medical history included relevant diagnoses including any surgical procedures with onset/resolutions dates.

3.6. Prior, Concomitant, and Follow-up Medications/Procedures

Any concomitant medication (including vitamin supplements, herbal remedies, and non-prescription medications) used while the subject was on study drug (up to 24 hours post first dose of study drug) was recorded. Concomitant medications were also collected through 14 days after the last dose of study drug.

Surgical medications were captured on the Surgical Medications page of the electronic Case Report Form (eCRF).

The concomitant/surgical medication name, dose (unit), start/end date and time, indication, frequency, and route of administration were recorded.

Surgical procedures were captured on the surgical procedure page of the eCRF and were to include type of procedure(s), date of procedure(s), and surgical start/stop time.

3.6.1. Prohibited Medications

The following medications were prohibited during the study:

- Preoperative opioids administered for a period of more than 72 hours in duration.
- Any investigational drugs other than oxymorphone HCl immediate-release oral liquid from 30 days prior to screening through End of Treatment (EOT).
- Oxycodone or oxymorphone within 48 hours prior to screening.
- Cough syrup containing an opioid from screening through EOT.
- MAOIs from screening through EOT.
- Products containing caffeine or xanthine.
- Non-opioid analgesics (acetaminophen and/or NSAIDs) during the Multiple-dose Phase.

3.7. Rescue Medication

All subjects were to receive rescue by morphine-NCA as needed. The dose of nurse-controlled analgesia (NCA) rescue medication was based on weight and age. NCA is an established form of postoperative analgesia, similar in nature to other demand-led analgesic regimens (e.g., patient-controlled analgesia [PCA]), but tailored for patients who are too young or unable to use PCA.

The morphine demand during the study was recorded including the start/end date and time, indication, dose (unit), frequency and route of administration.

3.8. Adverse Events

All adverse events (AEs) were collected by the investigator from the time of signing the informed consent/assent through 14 days after the last dose of study drug

3.8.1. Adverse Events Definitions

An AE was any unfavorable or unintended change in body structure (signs), body function (symptoms), laboratory result (e.g., chemistry, ECG, X-ray, etc.), or worsening of a pre-existing condition associated temporally with the use of the study drug whether or not considered related to the study medication. AEs include:

- Changes occurred in the general condition of the subject.
- Subjective symptoms offered by or elicited from the subject.
- Objective signs observed by the investigator or other study personnel.
- All concurrent diseases that occurred after the start of the study, which included any change in severity or frequency of pre-existing disease. Post-operative pain was captured as an AE after the EOT.
- All clinically relevant laboratory abnormalities or physical findings that occurred during the study.

3.8.2. Serious Adverse Events

Serious adverse events (SAEs) were those AEs that meet any of the following criteria:

- Resulted in death.
- Life-threatening event.
- Resulted in or prolongs an inpatient hospitalization.
- Resulted in permanent or substantial disability.
- Was a congenital anomaly or birth defect.
- Any important medical event that might have jeopardize the subject or might have required medical intervention to prevent one of the outcomes listed above.

3.9. Clinical Safety Laboratory Tests

Blood and urine samples were collected for testing the following clinical laboratory parameters at Pre-treatment and EOT (24 hours post dose) listed in Table 5.

Table 5: Clinical Laboratory Parameters

Hematology	Biochemistry	Urinalysis
Hemoglobin Hematocrit Red blood cell (RBC) White blood cell (WBC) Platelets WBC Differential	Glucose Sodium Potassium Calcium CO ₂ Inorganic phosphate Blood urea nitrogen Creatinine Aspartate transaminase (AST) Alanine transaminase (ALT) Gamma-glutamyl transferase (GGT) Total bilirubin (TBL) (direct bilirubin reflex if elevated) Albumin Alkaline phosphatase (ALP)	Glucose Protein Specific gravity Nitrite Blood ^a Leukocytes ^a

^a Microscopic examination will be performed if blood or leukocytes are detected by dipstick.

Any new clinically significant laboratory abnormality observed, were considered as an AE or SAE as appropriate.

3.10. Vital Signs

Vital sign measurements included systolic and diastolic blood pressure, respiratory rate, pulse, body temperature, and oxygen saturation. Length (height) and weight were recorded at screening only and body mass index (BMI) will be computed. Refer to Table 8 for BMI derivation.

For the single-dose phase, vital sign measurements were taken at Screening, post-surgery evaluation visit, baseline visit, 0.5, 1.0, 1.5, 2.0, 3.0, 4.0, 6.0, 8.0 and 24-hours post dose.

For the multiple-dose phase, vital sign measurements were taken at Screening, post-surgery evaluation visit, baseline visit, 0.5, 1.0, 2.0, 3.0 and 4.0 hours after administration of first dose of study drug; and at 0.5, 1.0 and 2.0 hours after administration of subsequent doses.

Clinically significant abnormalities (as per Investigator’s criteria) in vital sign values were considered as an AE or SAE as appropriate.

3.11. Physical Examination

A complete physical examination (by body system) was conducted at Screening or pre-dose evaluation. A brief physical exam excluding height and weight was performed at the EOT assessments. The physical examination evaluation included an examination of abdomen, extremities, general appearance, genitourinary, heart, HEENT, lungs, lymphatic, musculoskeletal, neck, neurological, skin, thorax and other conditions of note. Physical examination findings were recorded as normal, abnormal or not done.

Clinically significant abnormalities (as per Investigator’s or Sponsor’s criteria) in physical examination findings were to be considered as an AE or SAE as appropriate.

3.12. Respiratory Function

All subjects were monitored for the appearance of respiratory symptoms through monitoring of oxygen saturation, heart rate, respiratory rate, apnea monitoring, and administration of an opioid antagonist (e.g. Naloxone).

Any appearance of respiratory symptoms were to be monitored not only at the time of scheduled assessments, but as needed throughout the study duration.

An AE or SAE was to be recorded, as appropriate, if any of the following occur:

- Oxygen saturation decreased to $\leq 90\%$
- Heart rate decreased to $\leq 50\%$ of the expected norm for age
- Respiration rate decreased to $\leq 50\%$ of the expected norm for age
- Any episodes of apnea
- Any administration of an opioid antagonist to treat respiratory depression

3.13. Neurological Function

All subjects were to be monitored for the appearance of central nervous system (CNS) symptoms by monitoring the level of sedation through the Modified Ramsay Sedation Scale. Neurological assessment (level of sedation) will be considered as an SAE if the score is >6 on the Modified Ramsay Sedation Scale. Table 6 describes the scores and the definitions of the Modified Ramsay Sedation Scale.

Table 6: Modified Ramsay Sedation Scale

Score	Definition
1	Awake and alert, minimal or no cognitive impairment
2	Awake but tranquil, purposeful responses to verbal commands at conversation level
3	Appears asleep, purposeful responses to verbal commands at conversation level
4	Appears asleep, purposeful responses to verbal commands but at louder than usual conversation level or requiring light glabellar tap
5	Asleep, sluggish purposeful responses only to loud verbal commands or strong glabellar tap
6	Asleep, sluggish purposeful responses only to painful stimuli
7	Asleep, reflex withdrawal to painful stimuli only (no purposeful responses)
8	Unresponsive to external stimuli, including pain

3.14. 12-lead Electrocardiogram

12-lead electrocardiogram (ECG) were collected as part of the screening assessments which included the overall interpretation of ECG as normal, abnormal – not clinically significant and abnormal – clinically significant along with the abnormality details.

3.15. Pharmacokinetic Assessments

The SAP for this abbreviated CSR includes safety assessments only. All PK assessments planned in the protocol were removed. This change is included in the Change from Protocol Section of the SAP.

4. STUDY PARAMETERS

4.1. Subject Disposition

Subjects were considered to have completed the study if they completed the 14-day follow-up telephone call. EOT procedures were completed per schedule of assessments for subjects who discontinued from the study for any reason, the reason and date for early discontinuation was also be recorded in the eCRF. In case discontinuation is due to subject withdrawal of consent, no EOT procedures were performed except the collection of AE information.

Screen failures were recorded in the eCRF.

4.2. Demographics and Baseline Characteristics

Demographics and baseline characteristics included the following parameters:

- Age
- Height (at Screening)
- Body weight (at Screening)
- BMI in kg/m² (at Screening)
- Gender
- Race
- Ethnicity

4.3. Protocol Deviations

Protocol deviations will be identified and documented prior to database lock. Protocol deviations observed and recorded during clinical monitoring reports will be considered; deviations will not be determined programmatically.

The Endo study team will approve all final protocol deviation assignments and classify them as either major or minor during a protocol deviation review meeting held prior to the database lock.

4.4. Prior, Concomitant and Follow-up Medications

All medications will be coded using World Health Organization (WHO) Drug Dictionary Version March 2016, by active ingredient and anatomical therapeutic chemical (ATC) classification of ingredients.

A prior medication is defined as any medication taken within the 30 days prior to signing consent.

A concomitant medication is any medication starting on or after the informed consent is signed for this study and up to 24 hours post last dose or early termination (ET).

A follow-up medication is any medication starting after 24 hours post last dose through the 14-day follow-up period.

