Table 4) will be collected following randomization. The FLACC will be used for subjects in Groups A and B. The NIPS will be used for subjects in Groups C and D. All subjects will then be closely monitored for pain and their pain score will be recorded at least hourly until their pain score is ≥ 4 on the FLACC or ≥ 3 on the NIPS, at which time they will be administered study drug (oxymorphone HCl immediate release oral liquid for Groups A and B; IV oxymorphone HCl for Groups C and D) or placebo. Subjects in Groups A and B must be able to tolerate oral intake prior to receiving oxymorphone oral liquid. Morphine-NCA (section 8.1.4) will be initiated coincident with but not earlier than study drug/placebo administration, and this time will be designated as day 1 time zero. No food or oral liquid restrictions will be imposed around the time of dosing. All subjects will receive morphine-NCA rescue as needed. Subjects will undergo subsequent pain assessments at half-hour intervals post first dose in the multiple-dose phase (Table 4). Following dose 1, subsequent doses should be administered q4-6h PRN but no less than 4 hours apart, and at least 20 minutes have elapsed since the last bolus NCA rescue. The last dose of study drug will be administered no later than 18h post first dose. (All subjects must receive a minimum of 3 doses of study drug in the multiple-dose phase). PK and additional assessments will occur at fixed intervals throughout the multiple-dose phase, as outlined in section 3. Food consumption will be recorded from the period 1 hour prior to administration of study drug through EOT assessment; record all times that any food was consumed and what food was consumed (DAT, DAT-soft, FF, CF, water, formula, breast milk).

Following first administration of study drug, procedures and assessments will include the following:

- Blood samples for PK analysis should be collected immediately prior to each dose. Post-dose vital signs, respiratory assessments, and neurological assessments will be recorded at 0.5, 1, 2, 3, and 4 hours after administration of first dose of study drug; and at 0.5, 1, and 2 hours after administration of subsequent doses.
- Continuous telemetry.
- Continuous pulse oximetry.
- AEs and concomitant medications will be monitored throughout the multiple-dose phase.
- Pain assessments (using FLACC or NIPS; see Appendix C or Appendix D, respectively) will be recorded every 0.5 hours through EOT.

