5. ANALYSIS POPULATIONS

This study was terminated early. Baseline assessments and safety assessments will be summarized using the Safety Population. Table 7 describes the analysis populations used to describe safety assessments in this study.

Table 7: Analysis Populations

Population	Definition	Displays
Single-Dose Safety Population	The Safety Population of the single-dose phase includes all subjects who receive at least 1 dose of study drug in the single-dose phase.	All safety analyses and demographic/baseline characterization for the single-dose phase will use this population.
Multiple-Dose Safety Population	The Safety Population of the multiple-dose phase includes all subjects who receive at least 1 dose of study drug or placebo in the multiple-dose phase. Subjects will be attributed to the treatment that they actually received regardless of their assigned randomized treatment.	All safety analyses and demographic/baseline characterization for the multiple-dose phase will use this population.
Overall Safety Population	Includes all the subjects in the Single-dose Safety Population and the Multiple-dose Safety Population	All the subject listings except disposition listings will use this population. Disposition will be based on all subjects enrolled.

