6.3.1.2. Concomitant Status of Medication for Completely Unknown Start Date

The following rules will apply in cases where start date of concomitant medication is completely unknown:

- If the medication onset date is unknown and the end date/time is after the screening date but on or before 24 hours post first dose or the medication is ongoing, then the medication will be considered as concomitant.
- If the medication onset date is unknown and the end date/time is before the screening date, then the medication will not be considered as concomitant.
- If both the start and end dates are unknown, then the medication will be considered as concomitant. This approach is the most conservative following the worst-case principle.

If the medication onset date is partly present and month/year is prior to the first dose, then the medication will be considered as concomitant.

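### SAP 4.4 and 6.3.1.2 classify the same medication differently depending on how complete its start date is, some records meet no rule, and Table 8 numbers the dosing day both 0 and 1

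*SAP*

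**What the plan says.** SAP 4.4 defines three classes.

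- Prior: "A prior medication is defined as any medication taken within the 30 days prior to signing consent".
- Concomitant: "A concomitant medication is any medication starting on or after the informed consent is signed for this study", with the window running "up to 24 hours post last dose or early termination (ET").
- Follow-up: a start later than 24 hours after the last dose, through the 14-day follow-up.

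It does not say whether the classes are exclusive.

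SAP 6.3.1.2 deals with incomplete start dates. With a completely unknown start, a drug is concomitant if its end is "after the screening date but on or before 24 hours post first dose or the medication is ongoing". It is not concomitant if it ended before the screening date, and it is concomitant if start and end are both unknown. One further rule covers partial starts: "If the medication onset date is partly present and month/year is prior to the first dose, then the medication will be considered as concomitant".

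On collection, SAP 3.6 states: "Concomitant medications were also collected through 14 days after the last dose of study drug". SAP 7.5 plans frequency tables by ATC class and active ingredient, and a listing that shows the classification. SAP 6.1 lists all eCRF data and derived variables.

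SAP 6.2, Table 8, sets the first-dose day as relative Day 1. It defines Study Day as the assessment date minus that day, and AE Onset Day as the AE start date minus the first-dose date plus 1.

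**The concern.** A rule for missing dates should approximate the answer the full date would give. Here it reverses it. The complete record is left out of the concomitant class, while the incomplete record of the same drug is put in. Reading the classes as non-exclusive does not help, because the fully dated drug still fails the concomitant definition.

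This SAP reports safety only, after a study stopped on IDMC advice about respiratory depression, and the concomitant table is where a reader looks for co-exposure. Protocol 10.2 allows CNS depressants, muscle relaxants and antihistamines that were given regularly beforehand to continue at a stable dose. If begun before consent and fully dated, they would be missing from that table. Cohorts and randomized arms are planned at 5 subjects per age group, so one misclassified subject moves a frequency by 1/5 = 20 percentage points.

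The Table 8 slip means one calendar date can carry two different day numbers in the listings.

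**Working it through.** The plan gives no figure to reproduce here except the label Day 1 for the first-dose day. The check applies the stated rules literally to an illustrative subject. The dates are assumptions: consent and screening on 15 May, first dose on 20 May at 08:00.

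**1. A drug started 20 April and ongoing at dosing**

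| Start date as recorded | Rule | Result |
|---|---|---|
| 20 April (complete) | 4.4: start is before 15 May | prior, not concomitant |
| Unknown | 6.3.1.2: ongoing | concomitant |
| April only | 6.3.1.2: month/year before first dose | concomitant |

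**2. No stop-date check for partial starts.** A start recorded as April with a stop on 16 April is concomitant. The stop is 29 days before consent (16 April to 15 May) and 34 days before dosing (16 April to 20 May). With a completely unknown start, the same stop date makes the drug not concomitant.

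**3. Partial start in the dosing month.** May is not before the month of first dose, so no rule applies. The days from 30 days before consent (15 April) to the day before dosing (19 May) number 16 in April plus 19 in May, 35 in all. A start on any of the 19 May days with the day missing is unclassified. This share depends on the calendar. With consent on 28 April and first dose on 2 May, the span is 29 March to 1 May (3 + 30 + 1 = 34 days), and only 1 day falls in the dosing month.

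**4. Unknown start, known end more than 24 hours after first dose.** No rule applies; an end 3 days after dosing is an example. Let L be the hours from first to last dose. Collection runs to 14 days after the last dose, so the uncovered span is (14 + L/24) − 1 = 13 + L/24 days.

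**5. Window end.** SAP 4.4 ends at L + 24 hours after first dose (no early termination) and 6.3.1.2 at 24 hours, so they differ by L hours.

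The range of L comes from the documents. In the single-dose phase L = 0. In the multiple-dose phase the Safety Population "includes all subjects who receive at least 1 dose of study drug or placebo in the multiple-dose phase", so L can be 0, and Protocol 8.1.6 puts the last dose no later than 18 hours after the first. The same section says "All subjects must receive a minimum of 3 doses of study drug in the multiple-dose phase", no less than 4 hours apart, so L is at least 2 × 4 = 8 when that is met.

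| L (hours) | Window ends differ by | Span with no rule (step 4) |
|---|---|---|
| 0 | 0 h | 13.00 days |
| 8 | 8 h | 13.33 days |
| 18 | 18 h | 13.75 days |

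**6. Table 8 day numbers**

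| Date | Study Day (date − 20 May) | AE Onset Day (date − 20 May + 1) |
|---|---|---|
| 19 May | −1 | 0 |
| 20 May (first dose, relative Day 1) | 0 | 1 |
| 21 May | 1 | 2 |

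The two labels differ by 1 on every date.

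**The case against.** The strongest case on the other side is about consequence, not reading.

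- The report is abbreviated and descriptive. Five subjects were enrolled in Group B and none in Groups C or D. With Group A planned at no more than 15 single-dose and 10 multiple-dose subjects, about 15 + 10 + 5 = 30 are involved, and every record can be inspected in the listing.
- SAP 3.6 and Protocol 8.1.3 describe collection in terms of use and ongoing medications, so 4.4 may simply be loosely worded.
- SAP 3.6 says start and end dates and times were recorded, so incomplete records may be few or none.
- The 19-of-35 figure comes from the chosen calendar.
- Study Day drives no analysis in SAP section 7.

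Much of this stands as a limit on size. Drugs started after consent, including perioperative ones, are classified correctly when fully dated. Rescue morphine has its own summary (SAP 7.7). Overlap with dosing can be read by hand from the listed dates.

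It does not remove the fault. The main error affects complete dates, so it does not depend on how many dates are missing. The use-based collection wording supports correcting 4.4; it does not change what a programmer following 4.4 would produce. Listing both dates does not correct a count in a table.

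Two details are fair additions. The phrase about 24 hours after first dose also stands in SAP 3.6. An unknown start with an end on the screening date itself also meets no rule.

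**Conclusion.** The concern holds and should be corrected before the medication tables are run. Followed exactly, the SAP leaves a pre-consent drug still in use at dosing out of the concomitant counts when its start date is complete. It counts a drug that stopped before consent when the start is partial and the month and year precede first dose. It gives no classification for partial starts in the dosing month, or for unknown starts with a known end more than 24 hours after first dose. The two window ends agree in the single-dose phase. In the multiple-dose phase they differ by 0 to 18 hours without early termination, or 8 to 18 hours when the required three doses are given. Study Day and AE Onset Day differ by 1 throughout.

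The effect is limited to descriptive tables, listings and day labels. The day counts in steps 2 and 3 rest on the assumed calendar; the classification conflict does not. The documents do not give the number of records with incomplete dates, so the number of misclassified records cannot be estimated.

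**What to change.** - **SAP 4.4:** add to the concomitant definition medications started before consent and ongoing at or after consent, and state that these count as both prior and concomitant. Counting in both classes is a convention, but the SAP must state one.
- **SAP 6.3.1.2, window:** replace the limit of 24 hours after first dose with 24 hours after last dose or early termination. Note in SAP 3.6 that its first-dose phrase describes collection and that classification follows 4.4.
- **SAP 6.3.1.2, default:** treat an unknown or partial start as concomitant unless the stop date shows that use ended before consent/screening, or the known part of the start shows that it began after the window. This covers stop dates after the window, partial starts in the dosing month, and an end on the screening date.
- **SAP 6.2, Table 8:** compute Study Day as date minus first-dose date plus 1 on or after dosing, without the plus 1 before dosing, and use the same rule for AE Onset Day.

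The cost is SAP wording and a few lines of programming. No new data are needed.
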